**The Feasibility, Usability, and Acceptability of Using the Oculus™
Virtual Reality Gaming Technology in Stroke Survivors for Upper Extremity and
Cognitive Rehabilitation**

NCT05672628

Version Date: 03/06/2024

Protocol Title: The Feasibility, Usability, and Acceptability of Using the Oculus™ Virtual Reality Gaming Technology in Stroke Survivors for Upper Extremity and Cognitive Rehabilitation

Principal Investigator: [name]

Co-Investigators: [name], DO; [name]; [name], OT; [name], SLP; [name]; [name] MD

Population: Stroke survivors and caregivers (n= 20 dyads) reflecting a range of stroke subtypes, disabilities, and races/ ethnicities will be recruited.

Number of Sites: 1 – Aging in Place (AIP) apartment, University of Texas Health Science Center at Houston

Study Duration: November 2022 – October 2023

General Information

- Primary Specific Aims (See Figure 1):
 - **S.A.1.** To test the (a) feasibility, (b) usability, and (c) acceptability of using the Oculus VR for chronic stroke survivors (6 months-5 years) who have mild-moderate cognitive and unilateral arm impairment to administer upper extremity and cognitive rehabilitation (n=20 dyads).-
 - **SA 2:** To calculate the change in upper extremity (Fugl-Meyer, ARAT) and cognition (MoCA) scores on standardized measurements per standard of care (n=20 dyads).
 - **S.A.3.** To qualitatively explore the impact of engaging caregivers in supporting the stroke survivor's rehabilitation and the impact of this engagement on the stroke survivor and caregiver dyad using semi-structured interviews. (n=20 dyads).
- Objectives:
 - Our overall objective in this application is first to determine whether Oculus VR is feasible, usable, and acceptable to stroke survivors who have chronic mild-moderate cognitive and upper extremity deficits. Our secondary objective is to explore the impact of the rehabilitation sessions using the Oculus VR on the caregiver-stroke survivor dyad

Background/Significance

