- We believe that this study will generate an estimate of the effect that can be used to inform the development of randomized controlled studies (RCTs).
 - This study will also generate RCTs examining the use of the Oculus VR as a form of stroke rehabilitation that is scalable to the participant's home setting.
 - There are few studies that have examined the role of caregiver engagement on the success of remote stroke rehabilitation.
- The caregiver will be encouraged to use Caregiver Cues (Appendix D) as this will help the caregiver to engage with the participant using encouragement or positive cues to the stroke participants to support them during the session.
- The therapist or RA (who will be trained by the therapist) who is conducting the session will use the Therapist Guided Cues (Appendix E) to guide the stroke participant with problem solving and planning for performing home exercises that will be provided to the participant at the first session.
- The data we obtain from caregivers and stroke survivors (dyads) will inform future studies that examine ways to best support the dyads to improve stroke rehabilitation outcomes and reduce stress in the caregivers. (See Appendix F)

Statistical Analysis

- To address S.A.1., feasibility, usability, and acceptability of the Oculus VR headsets for upper extremity and cognitive therapies will be analyzed as follows: Feasibility: Assessed from the number sessions attended and time spent using the Oculus VR. The minimum number of sessions expected for a user are 2 per week (8 sessions) and the minimum time spent playing Job Simulator is 1 hour per week (4 hours) through the end of the study. Descriptive statistics of the participation rates and measures including frequencies, median and interquartile ranges for sessions attended and time spent using the game. Usability: Descriptive statistics for demographic and clinical data and participant scores on the SUS and PQ will be calculated. (See Appendix G and H) We will refrain from using inferential statistics since this is a pilot study and hypothesis testing is not the objective. Acceptability: Descriptive statistics for scores on the SSQ will be calculated at baseline and after each session (See Appendix I). We will examine the trend of symptoms for each participant.)

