- To address S.A.2. As part of standard of care, we will calculate change in arm and cognitive scores for each stroke participant from the following tests: MoCA, FM, and ARAT. (See Appendix J, K, and L) After inspection of the distribution, either the paired t-test or the nonparametric Wilcoxon signed rank test will be used to evaluate the significance of the difference score. However, statistical inference is not the primary interest of this pilot study. The effect size provided by Cohen's d measure, i.e., the standardized difference of mean score, will provide a preliminary measure of the effectiveness of Oculus VR in this pilot study. Similarly, standardized differences in the BSFC-s scores will provide the effect sizes for the change in caregiver burden.
- To address S.A.3., interview data will be analyzed following methods for thematic analysis.^{34,35} Using a qualitative data analysis program, Atlas.ti,³⁶ 2 researchers will review transcripts to gain a sense of the whole, identify codes, categories, and generate higher order themes to describe

the role of caregiver engagement during the session. Reasons for non-participation will be obtained from those eligible participants who decline participation. Unacceptable components and reasons for non-participation will be considered in the planning and designing of future trials.

Outcomes

- Upon completion of these aims, the expected outcomes are to develop randomized control trials (RCTs) to determine the effectiveness of the Oculus VR for stroke rehabilitation. We anticipate using the information from the dyadic interviews to develop qualitative studies and RCTs examining the role of the caregiver on remote stroke rehabilitation outcomes.
- Please see Table 1 (below) for the outcomes with timepoints.

Primary and Secondary Outcomes with Timepoints			
Primary	Timepoint	Secondary	Timepoint
MoCA (Appendix J)	Baseline and Last Session	Pre-Intervention Questionnaire (Appendix R)	Baseline Session
Fugl-Meyer (Appendix K)	Baseline and Last Session	Therapy Follow-Up Checklist (Appendix M)	Session 2 – Last Session
ARAT (Appendix L)	Baseline and Last Session	Post-Intervention Questionnaire (Appendix S)	Last Session
Caregiver Burden Scale (for caregiver only; Appendix F)	Baseline and Last Session		
Simulator Sickness Questionnaire (Appendix I)	Session 1 – Last Session		
System Usability Scale (Appendix G)	Last Session		
Presence Questionnaire (Appendix H)	Last Session		

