Number of sessions attended; Duration (minutes) of session	Session 1 – Last Session		

Table 1

Potential Problems and Alternative Approaches

- If the participant cannot complete the study, then we will offer home exercises selected by the therapist from Appendix N and they will exit the study.
- Stroke survivors will be encouraged to take a brief break every 20 minutes due to potential for visual fatigue. If the participant develops simulator sickness (e.g., nausea, dizziness, etc.) or wishes to stop the session for any reason, we will immediately stop the session and allow the participant to rest until the symptoms subside.
 - If the participant's symptoms do not resolve immediately, then we will take the patient's blood pressure, pulse, and/ or temperature as appropriate.
 - We will call 911 should the participant require immediate assistance. If the participant does not require immediate care, we will encourage the participant to be evaluated at an urgent care and/ or their doctor's office.

- All adverse events will be monitored, documented, and reported to the ethics committees. Progress addressing adverse events will be recorded until their resolution.

Data Management

- We will record the Oculus gaming sessions using the camera located in the living room for the therapists to review after the session to evaluate the participants' progress.
- Informed consent documents and de-identified, demographic and participant satisfaction surveys will be stored electronically via REDCap,™ following UTHealth security procedures. Qualitative interview data will be digitally recorded; these raw audio files will be stored in a secure folder of the PI's UTHealth, OneDrive. Transcribed, de-identified interview data will be managed and analyzed via Atlas.ti.™

Collaboration and Interaction Plan

- The proposed interdisciplinary project brings together highly experienced investigators in diverse areas of research and clinical practices.
- The project is built from developing new collaborations between investigators across institutions including the University of Texas Health Science Center at Houston (UTHealth).
- The team will be led by

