- The data will serve as preliminary data for subsequent competitive, peer-reviewed extramural grant applications that address telerehabilitation in stroke survivors within the home and the role of their caregiver.
 - Specifically, the proposed project addresses priorities outlined by institutes (e.g., National Institute of Neurological Disorders and Stroke, National Institute of Aging and National Institute of Nursing Research) within the National Institutes of Health (NIH) by investigating innovative approaches to promote health and well-being in patients and their informal caregivers living within the confines of a chronic disease. Specifically, stroke survivor acceptability data and knowledge derived from commercially available VR headset technology are needed to demonstrate:
 - The technology is acceptable for at-home use in stroke populations
 - The technology is capable of effecting improvement in upper extremity motor movement and cognition in stroke survivors.
- We will use the data from the proposed project to determine and complete the needed modifications to the home rehabilitation program using the Oculus VR headset in the post-stroke population.
- The data from this study will be used to plan an RCT to test the effectiveness of the intervention on improving upper extremity functionality and cognitive outcomes that can lead to improved independence during activities of daily living.
- We also plan to examine the role of the caregiver on home rehabilitation outcomes and the impact of caregiver participation during home rehabilitation sessions on stroke survivor-informal caregiver dyads and on caregiver burden.
- We anticipate submitting grant applications to the NIH and other appropriate foundations within 3 months from the time this project is completed.

References

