Appendix E

Therapeutic Guided Cues Protocol^{12,13} for the Stroke Survivor Participants to be Used by the Research Assistant .

During the session:

Problem solving:

- What will you gain by doing exercises at today's session?
- (Reinforce with the patient) Flexible coping strategies include:
 - define the problem and goal
 - generate multiple solutions
 - select a solution
 - implement and evaluate

Decision making:

- What will you do if you start to feel dizzy or not well during today's session?

Resource utilization:

- How will you seek assistance from your caregiver today during the session?
- You can ask me to assist you during the session. How will you signal to me that you want to stop?

Partnership with rehabilitation therapist/ RA:

- Do you understand what I am asking you to do?
- Would you like to practice the arm/ hand movements (or using the hand controller) with me before starting the session?

Planning and taking action:

- How will you use the hand controller?
- How will you put the headset on? Who will assist you?
- How many times this week will you come to the AIP apartment for your rehabilitation session?

For arm/ hand exercises at home:

Problem solving:

- What will you gain by doing arm/ hand exercises at home?

Decision making & Planning and taking action:

- Where/ when/ what/ how will you do your arm/ hand exercises?
- How will you know if you are doing your arm/ hand exercises correctly?
- How will you know when to stop doing your hand/ arm exercises?

Resource utilization:

- Can a friend or family member assist you with your arm/ hand exercises?
- Do you have a non-slippery surface at home where you can do your exercises?
- Do you have slip-resistant shoes?

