Appendix M
Therapy Follow Up Checklist

**Please answer the following questions regarding therapy visits
that have been received since the last study visit**

Occupational Therapy	YES/NO	# of sessions	Session Length
Therapy addressed:	 Home exercise program  Self-care (dressing, toileting, etc)  Household tasks (cooking, cleaning, etc)  Return to worktasks  Coordination  Community tasks (shopping, using public transportation, etc)  Cognition (memory, multi-tasking, attention, etc)	 Transfers  Casting/splinting  Vision  Sitting/standing balance  Arm/hand exercises - Number of repetitions: _____	
Physical Therapy	YES/NO	# of sessions	Session Length
Therapy addressed:	 Walking  Running  Vestibular exercises  Leg exercises - Number of repetitions: _____	 Rolling in bed  Standing balance  Transfers  Casting/bracing - Number of repetitions: _____	 Sitting balance  Home exercise program  Getting in/out of bed  Core exercises - Number of repetitions: _____
Speech Therapy	YES/NO	# of sessions	Session Length
Therapy addressed:	 Cognition (memory, multi-tasking, attention, etc)  Communication (speaking and/or understanding)  Swallowing		

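### The S.A.2 effect size is labelled as effectiveness of Oculus VR, but it measures change under the whole study programme, including home arm exercises that the study itself provides

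*Combined protocol and SAP*

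**What the plan says.** Aim S.A.2 in General Information is modest: "To calculate the change in upper extremity" and cognition scores. The S.A.2 paragraph of Statistical Analysis goes further. It plans a paired t-test or Wilcoxon signed rank test on the difference scores, adds that inference is not the main interest, and then states that Cohen's d "will provide a preliminary measure of the effectiveness of Oculus VR in this pilot study". MoCA, FM and ARAT are all covered by that sentence.

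The Intervention section describes more than VR sessions. Caregivers are encouraged to use cues (Appendix D). The therapist or a trained research assistant uses guided cues (Appendix E) to help the participant plan for "performing home exercises that will be provided to the participant at the first session". Appendix E has a separate block on this, opening with "What will you gain by doing arm/ hand exercises at home".

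The same section expects the study to yield an effect estimate for designing randomized trials. The documents differ on what those trials would test. Outcomes says they are "to determine the effectiveness of the Oculus VR for stroke rehabilitation". The text on follow-on grants, just before the References, says the data will be used to "plan an RCT to test the effectiveness of the intervention".

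**The concern.** The label on d names one component, while the participant receives several. A reader planning the next trial would naturally take d as a device effect.

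If that trial tests VR without the home exercises, d describes a different treatment. If it tests the package, the planner needs to know which exercises were issued and how much was done, and the plan does not clearly capture either. Retest effects and outside therapy also contribute to any single-arm change. Home exercise differs from those in that the study supplies it, so the study can name it and record it.

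**Working it through.** The plan states no target effect, SD, alpha or power, so there is no figure to reproduce. The check sets the texts side by side.

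**1. What d estimates.** There is one group of 20 stroke survivors, measured at baseline and at the end, with no comparator and no adjustment. Taking the contributions as additive for illustration:

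mean change = VR sessions + home exercise + cues + outside therapy + retest and time effects

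and d = mean change / SD. The data give only the total on the left, so no single term can be read off.

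**2. Timing.** Appendix Q places FM and ARAT at session 1 and again at session 12, in week 4. The exercises are provided at session 1 and done at home afterwards, so they fall inside the measured interval.

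**3. Target.**
- FM and ARAT score the arm and hand, and the Appendix E home block concerns arm and hand exercise. The overlap is direct.
- MoCA is not the target of arm exercise. However, the problem-solving and planning cues in Appendix E, the caregiver cues in Appendix D, and any outside cognitive or speech therapy (both listed in Appendix M) run alongside VR. The VR-only label does not fit MoCA either.

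**4. Which exercises.** The Intervention text cites no appendix for the exercises themselves. Appendix N, whose title says the therapist selects them, is the likely source, but that is an inference. The body text ties it only to early leavers: "If the participant cannot complete the study, then we will offer home exercises selected by the therapist from Appendix N". The session-1 list in Appendix Q has no step for issuing exercises.

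**5. Where exercise done alone could be recorded.**
- Feasibility log: sessions attended and session minutes only.
- Appendix M, sessions 2 to 12: it has a home-exercise tick-box and an arm/hand repetitions field, but both are listed as therapy content under a heading that begins "Please answer the following questions regarding therapy visits". A participant with no outside visit has no clear place to answer.
- Appendix R: baseline history, collected before or at session 1.
- Appendix S: asks about VR, home use of the headset and the relationship, not about exercise done.

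**6. Cost of recording.** Sessions 2 to 12 give 11 checklists per participant. 11 x 20 = 220 answers, plus 20 session-1 entries = 240 at most.

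**The case against.** The strongest reply is that the plan already hedges. It calls d preliminary, says inference is not the main interest, puts feasibility, usability and acceptability first, and leaves effectiveness to later trials. No decision rule or sample size depends on d. This keeps the severity low. It does not answer the point, because those phrases limit how certain the result is and leave unchanged what d is said to measure.

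A second reply is that Oculus VR is shorthand for the programme. The cues and home exercises do sit under Intervention, and the grant text speaks of the intervention. That reading is possible. If it is meant, saying so is the fix.

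A third is that every single-arm pilot has this limit, and that recording exercise in 20 people will not isolate VR. That is correct. The gain is an accurate label and detail for replication.

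A fourth is that home exercises are only for people who leave. That provision covers early leavers and does not cancel the statement that participants receive exercises at session 1.

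Three stronger readings are tempting and not supported:
- *That home exercise goes unrecorded.* Appendix M has relevant fields. The trouble is the heading above them, and a research assistant might still use them for exercise done alone.
- *That home exercise explains a known part of the FM or ARAT gain.* The documents give no figure from which a share or a point value could be worked out.
- *That the Appendix N doses show how much exercise is at stake.* The documents do not confirm that this set is issued, how many exercises are chosen, or how well they are followed. Nine exercises are legible while the appendix prints totals of 11 and 13. Repetitions do not convert to FM or ARAT points in any case.

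**Conclusion.** The point holds and is minor. For all three measures, d is change under the study programme and should not carry the name of one component. The case is clearest for FM and ARAT, where exercise supplied by the study acts on the same limb between the two assessments.

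No size of bias is claimed. The conclusion rests on two readings: that the Intervention text means what it says about exercises at session 1, and that the therapy-visit heading of Appendix M governs the fields beneath it. The first is firm. The second is fair but not certain, so the recording gap is best described as having no clear place rather than no place.

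**What to change.** 1. In the S.A.2 paragraph of Statistical Analysis, describe d for MoCA, FM and ARAT as *change under the study programme (VR sessions and cues, with home arm exercises, alongside any outside therapy)*, and drop the reference to effectiveness of Oculus VR.
2. Add an entry to the session-1 list in Appendix Q recording which exercises were issued.
3. Add one line to Appendix M, placed outside the therapy-visits heading, for home arm or hand exercise done alone since the last visit. Days would do, or repetitions to match the existing field.
4. Report this descriptively beside the FM and ARAT change, stating that it documents exposure for planning a randomized trial and does not separate a VR effect.

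The cost is one wording change and at most 240 short entries, with no new visit. The downside is that the effect can no longer be labelled as VR alone. The stated study period ends in October 2023, before the 03/06/2024 version date, so it is unclear whether the forms can still change. The wording change applies either way. If data collection is over, the report should say that home exercise done alone had no dedicated record.

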We will give the stroke survivor the Montreal Cognitive Assessment (MoCA) that will assess their cognitive capabilities. We will arrange a time to meet with them on a video call using the computer and this will take only 15 or 20 minutes.	
1. Cognition (MoCA) test completed (Primary Outcome; Appendix J)	
12th Session (Week 4, last session; in the event that the study participant and/ or caregiver are unable to complete any post-intervention items, we will request a video call to complete any missing items that were not completed on the last session at a time convenient to the stroke participant or caregiver)	Initial & Date completed

 _____ Research Assistant complete the Therapy Follow Up Checklist with Subject before the start of the session. (Secondary Outcome, Appendix M) _____ Have the stroke survivor complete the Simulator Sickness Questionnaire (SSQ) at the beginning and end of the last 1-hour session (Primary Outcome; Appendix I) _____ Complete the System Usability Survey (SUS) via REDCap (Primary Outcome; Appendix G) _____ Complete the Presence Questionnaire (PQ) (Primary Outcome; Appendix H) 	

 Complete the Cognition (MoCA) test (post-intervention, if not completed during the Pre-Last Visit) (Primary Outcome; Appendix J)	
 Complete the Fugl-Meyer Upper Extremity Assessment (post-intervention) (Primary Outcome; Appendix K)	
 Complete the Action Research Atm Test (ARAT) (post-intervention) (Primary Outcome; Appendix L)	
 Complete the Caregiver Burden Questionnaire (Primary Outcome; Appendix F)	
 Complete the Post-Intervention Questionnaire (Participant and Caregiver) (Secondary Outcome; Appendix S)	

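### SUS, PQ, the exit interview and a reason for leaving are not clearly scheduled for participants who stop early, so usability summaries would describe those who reach the last session

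*Combined protocol and SAP*

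**What the plan says.** **Timing of the measures.** Table 1 (Outcomes) gives the last session as the only timepoint for the SUS, the PQ and the post-intervention interview. Appendix Q puts all three under the 12th session; the entries for the two primary outcomes read "Complete the System Usability Survey (SUS) via REDCap (Primary Outcome; Appendix G" and "Complete the Presence Questionnaire (PQ) (Primary Outcome; Appendix H". Appendix A is looser: for the SUS and the interview it says only that they come after the intervention, with no session number. Its timing cell for the PQ is too broken in the available text to rely on.

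**Early stopping.** Potential Problems and Alternative Approaches has one rule for people who cannot finish: "participant cannot complete the study, then we will offer home exercises selected by the therapist from Appendix N and they will exit the study". It mentions no assessment and no record of the reason.

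**Recovery of missing items.** The 12th-session heading in Appendix Q reads "12th Session (Week 4, last session; in the event that the study participant and/ or caregiver are unable to complete any post-intervention items" and continues "we will request a video call to complete any missing items that were not completed on the last session".

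**Reasons.** Statistical Analysis, S.A.3, states: "Reasons for non-participation will be obtained from those eligible participants who decline participation". It adds: "Unacceptable components and reasons for non-participation will be considered in the planning and designing of future trials".

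**Analysis.** Statistical Analysis, S.A.1, plans descriptive summaries of SUS and PQ. It gives no analysis set, no denominator and no rule for absent scores.

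**The concern.** People who give up on a headset are a direct source of information on whether it is usable. If SUS and PQ are taken only from those who reach the end of the schedule, the summaries leave out the group most likely to have had difficulty. If leavers rate the headset lower, the reported usability is too favourable as a description of everyone who tried it.

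Two features make this worth attention even in a small descriptive pilot. First, a SUS or PQ score not taken around the time of exit cannot be reconstructed later. Second, the plan intends to carry unacceptable components into the design of later trials. The interview question on what would stop someone using the headset again (Appendix S) sits in the last-session interview, so under the schedule a leaver is not asked it. Someone who leaves for a reason unrelated to symptoms would have no scheduled record of why.

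**Working it through.** The plan gives no dropout rate, expected score or sample-size figure on this point, so there is no figure to reproduce. The check has three steps.

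**Step 1: what the schedule yields for each kind of participant.**

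| Information | Completes the 12th session | Post-intervention items left undone at the 12th session | Exits earlier |
|---|---|---|---|
| SUS, PQ | Scheduled (Table 1, Appendix Q) | Video call (Appendix Q) | Nothing stated |
| Interview | Scheduled | Video call | Nothing stated |
| Reason for leaving | Not applicable | Not applicable | Nothing stated; S.A.3 asks only those who decline |
| Session count and minutes | Logged (Appendix A) | Logged | Logged up to exit |
| Simulator Sickness Questionnaire | Every session | Every session | Sessions attended |
| Adverse events | Recorded | Recorded | Recorded |

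The gap is confined to the first three rows of the last column.

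**Step 2: coverage.** Assume all 20 planned stroke survivors start using the headset. With k leavers who give no scores, the number contributing to SUS and PQ is 20 − k, and each leaver removes 1/20 = 5%.

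- k = 2: 18 of 20 (90%)
- k = 4: 16 of 20 (80%)
- k = 6: 14 of 20 (70%)

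**Step 3: possible shift in mean SUS.** Let C be the mean among completers and E the mean that leavers would have given. The mean over all 20 is [(20 − k)C + kE]/20, so

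completer mean − mean over all = (k/20) × (C − E).

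Both k and C − E are assumptions. On the SUS range of 0 to 100 the shift is:

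| Leavers k | C − E = 0 | 10 | 20 | 30 |
|---|---|---|---|---|
| 2 | 0 | 1.0 | 2.0 | 3.0 |
| 4 | 0 | 2.0 | 4.0 | 6.0 |
| 6 | 0 | 3.0 | 6.0 | 9.0 |

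For example, k = 4 and a gap of 20 give (4/20) × 20 = 4.0 points. With no leavers, or leavers who score like completers, the shift is zero. If leavers scored higher, its sign would reverse. The table shows how the result depends on the assumptions and is not an estimate.

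**The case against.** **The timing may already be flexible.** Table 1 names the last session without a number, and Appendix A says only that the measures follow the intervention. Either could mean each person's own last session. This stands in part: it is wrong to say the plan rules out scoring leavers. But the operational checklist, Appendix Q, equates the last session with the 12th, and no section says what staff should do when someone stops before it.

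**The video call may cover leavers.** Its wording about being unable to complete post-intervention items does not exclude someone who never reaches the 12th session. Equally, it stands under that session's heading and refers to items missed then, while the exit rule does not mention it. It is ambiguous, and one sentence would settle it.

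**Other data describe leavers.** A reader might infer that nothing is known about people who leave. The documents do not support that: session logs, sickness scores at attended sessions and adverse-event records remain and may partly show why someone left. None of them measures usability.

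**Session counts.** Statistical Analysis states "The minimum number of sessions expected for a user are 2 per week (8 sessions", while Appendix Q numbers 12. A reader might take the difference of four as the size of this problem. It is not. On a two-per-week schedule the eighth session could itself be the last, and someone who attends only eight of 12 could still attend the 12th. The two passages are inconsistent in their own right, and the sponsor must reconcile them.

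**Simulator sickness.** A reader might also infer a loss of sickness data because the analysis text does not define its baseline. Appendix Q collects the form at the beginning and end of every session, so nothing is lost; that is a matter of wording.

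**Impact is not demonstrated.** S.A.1 is descriptive, and the SUS value of 68 in Appendix A is a guide to interpretation, not a decision rule. This stands, and it limits the weight of the point.

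**Conclusion.** The point holds as a gap in data collection and reporting. Followed as written, the SUS and PQ summaries describe participants who reach the last session, and no reason for leaving is scheduled for those who do not. It should be corrected because the remedy is cheap and bears on two S.A.1 primary outcomes, but it does not undermine the pilot.

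The certain part of the size is coverage: 5% of the planned 20 for each leaver without scores. The shift in the summaries is unknown in size and could be zero. A reader might infer that usability will be overstated; the documents support only that it may be, if there are leavers and they rate the headset lower.

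The conclusion rests on the visible text. Figure 1, the consent pages and part of the Collaboration and Interaction Plan were not available, and a withdrawal procedure could be described there. Confidence is medium.

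**What to change.** 1. **Table 1 and Appendix Q.** State that a participant who stops early is offered SUS and PQ at exit, and the interview if willing, by the existing REDCap and video-call route.
2. **Exit record.** Record the reason for leaving, with no reason given as an allowed answer.
3. **Statistical Analysis, S.A.1.** Report SUS and PQ for last-session completers, for early leavers and for everyone with a score, each with the number contributing out of all who used the headset. Keep the separate rows, because leavers have had less exposure.

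**Cost.** There is one short contact per willing leaver: 10 SUS items (Appendix A) plus 29 PQ items (Appendix H) = 39 items, longer with the interview. Some leavers will decline. The Recruitment section pays $60 of the $100 incentive at the final session and does not say what applies to leavers, so uptake may be low. Missing scores will be reduced, not removed, and the usability results may look less favourable.

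**Timing.** The stated study duration ends in October 2023 and this version is dated 03/06/2024; the status of data collection is not given. If it has ended, only the counts in item 3 and any reasons already on file can be applied.
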